10.6 STANDARDIZED FIELD SOBRIETY TEST (SFST)

The Standardized Field Sobriety Test (SFST) is a battery of three tests administered and evaluated in a standardized manner to obtain validated indicators of impairment, e.g. in persons who have used narcotics [\[R19-1364\]](#), [\[R19-1365\]](#). These tests were developed based on research sponsored by the National Highway Traffic Safety Administration (NHTSA).

The three tests of the SFST are:

1. Horizontal gaze nystagmus (HGN):

Hereby the investigator asks the subject to follow a torch light, moved horizontally about 25-30 cm in front of the subject's eyes, only with his eyes, i.e. without moving the head. Occurrence of a nystagmus is considered an abnormal finding.

2. Walk-and-turn (WAT):

In this test, the subject is directed to take nine steps, heel-to-toe, along a straight line, then turn on one foot and return in the same manner in the opposite.

The following signs are considered abnormal: the subject

- cannot keep balance while listening to the instructions
- begins before the instructions are finished
- stops while walking to regain balance
- does not touch heel-to-toe
- steps off the line
- uses arms to balance
- makes an improper turn
- takes an incorrect number of steps

3. One-leg stand (OLS):

[figure not shown]
The subject is instructed to stand with one foot approx. 10 cm off the ground and count aloud by thousands (one thousand-one, one thousand-two, etc.) until told to put the foot down (after 30 seconds).

Abnormal findings are:

- swaying while balancing
- using arms to balance
- hopping to maintain balance
- putting the foot down

Proprietary confidential information © 2021 Boehringer Ingelheim International GmbH or one or more of its affiliated companies

The SFST findings are assessed using the following table:

If the subject's score is within the shaded area the subject may not be discharged until the result of control test lies within the white area.

Proprietary confidential information © 2021 Boehringer Ingelheim International GmbH or one or more of its affiliated companies

10.7 SARS-COV-2/ COVID-19 RELATED BENEFIT-RISK ASSESSMENT AND RISK MITIGATION MEASURES

10.7.1 Introduction

Due to the COVID-19 pandemic early 2020, it was assessed (based on current knowledge) if treatment with BI 409306 and BI 425809, as well as lamotrigine and ketamine, may pose a higher risk associated with SARS-CoV-2 infection. The general risk of SARS-CoV-2/ COVID-19 in context of the trial population's underlying disease and common co-morbidities was assessed as well. In addition, risk mitigation measures were implemented to protect study participants and personal involved in clinical trials. This document summarizes the benefit-risk assessment and the measures in context of COVID-19 pandemic.

10.7.2 Benefit-Risk Assessment in Context of COVID-19 Pandemic

Risks in context of the trial medication

No additional risks related to administration of BI 409306 and BI 425809 have been identified. For details, refer to Benefit-Risk Assessments in context of COVID-19 pandemic for patients participating in clinical trials investigating BI 409306 [[c32968037](#)] and BI 425809 [[c32354247](#)].

The exact mechanism of action of lamotrigine have not been elucidated yet. Presumably, lamotrigine inhibits neuronal sodium channels, thereby stabilizing neuronal membranes and consequently modulating presynaptic transmitter release of excitatory amino acids (e.g., glutamate and aspartate). Ketamine is a non-competitive NMDA-receptor (NMDAR) antagonist. These effects are not expected to increase the risk of acquiring or progression of SARS-CoV-2/ COVID-19. So far, there is no evidence in the literature of increased risk of infection or severe illness upon treatment with lamotrigine or ketamine.

Considerations around drug-drug-interactions are not included in this benefit-risk assessment – for those it should be referred to the Investigator's Brochures of BI 409306 and BI 425809, Drug Label Information of lamotrigine (██████████) and ketamine (██████████), and the most recent label of the respective medication(s) used for treatment of COVID-19.

Risks in context of the trial population:

The study is planned in male healthy volunteers 18 to 55 years of age (inclusive). This population does not have co-morbid medical conditions that predispose to a higher risk of severe COVID-19. While it is understood that in general, older age is associated with more severe disease, mortality was highest amongst the oldest individuals (i.e. age ≥ 65) [[R20-1319](#)], who are not represented in this study population.

Procedure-related risks:

During COVID-19 pandemic, participation in this clinical study will increase the risk of SARS-CoV-2/ COVID-19 virus infection due to traveling to the trial site, overnight stays at the trial site and completing the protocol-defined procedures at the trial site during

Proprietary confidential information © 2021 Boehringer Ingelheim International GmbH or one or more of its affiliated companies

ambulatory visits and overnight stays. Therefore, this study will only be conducted after the COVID-19 situation has been managed and in accordance with the local public health precautions.

The risk mitigation plan has been set up at both trial sites that detail specific precautionary measures (e.g. hygiene rules, wearing of face masks and physical distance), screening for SARS-CoV-2, and discontinuation of trial treatment of subjects with confirmed SARS-CoV-2/ COVID-19 virus infection.

Summary:

The overall benefit-risk assessment of participation in this clinical study for healthy subjects remains unchanged, i.e. low as indicated in Section [1.4](#), after consideration of COVID-19 risks and implementation of mitigation strategies. Thus, this trial can be conducted after the COVID-19 situation has been managed and in accordance with the local public health precautions.

The investigators will take the totality of information related to each single subject and the local COVID-19 situation into consideration when performing the individual benefit-risk assessment on a case-by-case basis. Considering all aspects, the investigator will decide upon each subject's (continued) participation in the planned trial. BI as the sponsor, where required, will support the investigator in their decision finding. It is acknowledged that the investigator may decide to implement protocol deviations where this protects the safety, wellbeing and/or is in the best interest of the subject.

10.7.3 Risk Mitigation Measures in Context of COVID-19 Pandemic

10.7.3.1 Screening Period

Subjects with positive PCR test from nasal swab for SARS-CoV-2 and/ or any clinical symptom suggestive for COVID-19 virus infection at *screening examination (V1)* and each time within 72 hours prior to admission to trial site at *screening ketamine challenge (V2)* and *treatment period 1 (V3, if subjects leave the site premises after V2)* will be not eligible for this study.

The following measures will be performed:

- (1) Study participants will be informed about, and asked to agree to SARS-CoV-2/ COVID-19 specific requirements with their diagnostic, therapeutic, and legal implications
- (2) Evaluation of subjects for SARS-CoV-2/ COVID-19 will be performed at *screening examination (V1)* and each time not later than 72 hours prior to admission to trial site at *screening ketamine challenge (V2)* and *treatment period 1 (V3)*, including
 - Temperature assessment
 - Questionnaire and medical assessment
 - PCR test for SARS-CoV-2 from a nasal swab sample

10.7.3.2 Treatment Periods

Evaluation of subjects will be performed each time not later than 72 h prior to admission to trial site in *treatment periods 2 and 3 (V4 and V5)*, incl. temperature assessment, questionnaire and medical assessment, and PCR test for SARS-CoV-2 from a nasal swab sample.

In case COVID-19 is suspected in a subject during trial participation, a SARS-CoV-2 PCR test and other applicable diagnostic measures (if required, e.g. CT of lungs) will be initiated without delay.

- If COVID-19 virus infection is confirmed, the measures will include isolation, sponsor/ authority notification, contact tracing and other as appropriate. Subjects who discontinue treatment should undergo the EoTrial Visit, but only after recovery from COVID-19 is confirmed incl. negative SARS-CoV-2 viral testing in accordance to the local public health precautions.
- If COVID-19 virus infection is not confirmed by SARS CoV-2 PCR test and other applicable criteria, the treatment may be not discontinued, but the next treatment (if applicable) will be conservatively postponed for at least 10 days have passed since symptoms first appeared and at least 72 hours have passed since last fever without the use of fever-reducing medications and symptoms (e.g., cough, shortness of breath) have resolved. Ultimately, clinical judgement and suspicion of SARS-CoV-2 infection determine whether to discontinue the subject for trial treatment.

The Risk Mitigation and Response Plans fully describing the site-specific measures related to SARS-CoV-2/ COVID-19 (e.g. hygiene rules, wearing of face masks and physical distance) will be filed in the ISF.

10.7.4 Assessment of Adverse Events related to COVID-19

For any AE related to SARS-CoV-2/ COVID-19, please note the BI standard processes should be followed, meaning:

(1) If a SARS-CoV-2/ COVID-19 virus infection is associated with clinical symptoms (AEs):

- Report as a non-serious AE, if the serious criteria are not met
- Report as a SAE, if serious criteria are met – e.g., hospitalization, serious for medical reasons, or AE term describing the clinical symptoms is on the “always serious list”. The mere fact that someone is infected with the SARS-CoV-2/ COVID-19 should not lead to a judgement of seriousness

(2) If a SARS-CoV-2/ COVID-19 virus infection is not associated with clinical symptoms, meaning there is just a positive SARS-CoV-2 PCR test:

- Report as a (non-serious) AE, as a positive test means a subject has an infection

Proprietary confidential information © 2021 Boehringer Ingelheim International GmbH or one or more of its affiliated companies

11. DESCRIPTION OF GLOBAL AMENDMENTS

11.1 GLOBAL AMENDMENT 1

Date of amendment	25 Aug 2020
EudraCT number	n.a.
EU number	
BI Trial number	1289-0057
BI Investigational Medicinal Products	BI 409306, BI 425809
Title of protocol	A study in healthy men to test whether BI 409306, BI 425809 or lamotrigine can reverse the memory problems caused by ketamine
To be implemented only after approval of the IRB / IEC / Competent Authorities	
To be implemented immediately in order to eliminate hazard – IRB / IEC / Competent Authority to be notified of change with request for approval	
Can be implemented without IRB / IEC / Competent Authority approval as changes involve logistical or administrative aspects only	
Section to be changed	Title Page Clinical Trial Protocol Synopsis Flow Charts A-D Sections 1-9 Appendices 10.1, 10.3-10.7
Description of change	1. BI 425809 (T3) treatment arm has been added. Drug profile and B/R assessment related to BI 425809 have been described. 2. The number of total entered subjects has been increased to 36. 3. Randomisation of subjects will be conducted applying incomplete block design: each subject will receive R treatment and 2 of 3 randomly allocated T1 or T2 or T3. 4. Washout period between treatments has been increased to 11 days [REDACTED]. 5. Flow Charts B, C and D detailing procedures at screening examination, screening ketamine challenge and treatment days have been added; Flow Chart A (Summary) has been updated. 6. [REDACTED] will be implemented during the breaks between the CANTAB tests (pre-ketamine and during ketamine infusion) and in the start of ketamine infusion.

Proprietary confidential information © 2021 Boehringer Ingelheim International GmbH or one or more of its affiliated companies

		
8. Light breakfast and light snack (clear liquid) will be served not later than 5h and 2h accordingly before the start of ketamine infusion.
 
9. SARS-CoV-2 virus PCR tests are being implemented at screening examination and shortly before each admission to the study site.
 
10. Exclusion and Discontinuation of trial treatment criteria specific to SARS-CoV-2/ COVID-19 have been added.
 
11. B/R assessment and risk mitigation measures in context of COVID-19 pandemic have been summarized in Appendix 10.7.

Rationale for change		
1-5. Due to progress in clinical development, BI 425809 has been included as additional treatment (T3) in the study, which required further update of the study design.
 
8. Because of increased total duration of procedures at screening ketamine challenge and treatment days, meals will be served in order to avoid prolonged fasting and related to it common AEs.
 
9-11. Due to the COVID-19 pandemic, and given infected individuals may be clinically asymptomatic, the study design has been adapted to safeguard the subject's safety, and exclude infected volunteers from study participation.

11.2 GLOBAL AMENDMENT 2

Date of amendment	12 Nov 2021
EudraCT number	n.a.
EU number	
BI Trial number	1289-0057
BI Investigational Medicinal Products	BI 409306, BI 425809
Title of protocol	A study in healthy men to test whether BI 409306, BI 425809 or lamotrigine can reverse the memory problems caused by ketamine
To be implemented only after approval of the IRB / IEC / Competent Authorities	
To be implemented immediately in order to eliminate hazard – IRB / IEC / Competent Authority to be notified of change with request for approval	
Can be implemented without IRB / IEC / Competent Authority approval as changes involve logistical or administrative aspects only	
Section to be changed	1. Clinical Trial Protocol Synopsis 2. Flow Charts C-D 3. Section 3.3.3 4. Section 5.6.1.1
Description of change	1. Number of subjects in each treatment has been clarified. Criteria of normative performance on CANTAB PAL test have been clarified. 2. In Screening V2, admission of subjects is allowed in the evening before the screening ketamine challenge. In V2-V5, admission in the morning of ketamine challenge is also possible at discretion of the Investigator or designee. 3. Exclusion criteria have been clarified. 4. Methods of pharmacogenomics sample collection have been adapted to include requirements of the sites' local laboratories, as well as the central lab
Rationale for change	Changes are based on the need to facilitate and operationally adapt the procedures of Screening Visit 2 by including an overnight stay prior to screening ketamine challenge. With this amendment minor inconsistencies in the study protocol have been corrected and other protocol clarifications have been provided.

APPROVAL / SIGNATURE PAGE

[figure not shown]
[figure not shown]
[figure not shown]

2. LIST OF ABBREVIATIONS

Term	Definition / description
AE	Adverse Event
AESI	Adverse event of special interest
ALT	Alanine aminotransferase
AST	Aspartate aminotransferase
BI	Boehringer Ingelheim
BP	Blood pressure
CADSS	Clinician Administered Dissociative States Scale
CANTAB	Cambridge Neuropsychological Test Automated Battery
COVID	Coronavirus disease
C-SSRS	Columbia Suicidal Severity Rating scale
CTP	Clinical Trial Protocol
CTR	Clinical Trial Report
CV	Arithmetic coefficient of variation
DSST	Digit Symbol Substitution Test
ECG	Electrocardiogram
FU	Follow-up
gCV	Geometric coefficient of variation

Term	Definition / description
gMean	Geometric mean
ICH	International Conference On Harmonisation
IPD	Important protocol deviations
IQRMP	Integrated Quality and Risk Management Plan
MedDRA	Medical Dictionary For Regulatory Activities
MOAA/S	Modified Observer's Assessment of Alertness/Sedation
PAL	Paired Associates Learning
PK	Pharmacokinetic(s)
[REDACTED]	[REDACTED]
PD	Pharmacodynamic(s)
PDS	Pharmacodynamic set
[REDACTED]	[REDACTED]
PR	Pulse rate
RAGe	Report appendix generator
REP	Residual effect period
RPM	Report Planning Meeting
RVP	Rapid Visual Information Processing
SAE	Serious adverse event
SaO ₂	Oxygen saturation
SD	Standard Deviation
SFST	Standardized Field Sobriety Test
SOC	System Organ Class

Term	Definition / description
SWM	Spatial Working Memory
	[REDACTED]
	[REDACTED]
TS	Treated set
TSAP	Trial Statistical Analysis Plan
ULN	Upper limit of normal range
VA	Visual acuity
WHO	World Health Organization

3. INTRODUCTION

As per ICH E9 ([1](#)) the purpose of this document is to provide a more technical and detailed elaboration of the principal features of the analysis described in the revised CTP, and to include detailed procedures for executing the statistical analysis of the primary and secondary variables and other data.

This TSAP assumes familiarity with the CTP and its amendments. In particular, the TSAP is based on the planned analysis specification as written in CTP Section 7 "Statistical Methods and Determination of Sample Size". Therefore, TSAP readers may consult the revised CTP for more background information on the study, e.g., on study objectives, study design and population, treatments, definition of measurements and variables, planning of sample size, randomisation.

[figure not shown]
[figure not shown]
[figure not shown]
Study data as collected in the eCRF will be stored in a trial database within the RAVE EDC system. All study data also including external data will then be uploaded to the CDR data warehouse.

The statistical analyses will be performed within the validated working environment CARE, including SASTM (current Version 9.4, by [REDACTED]), and a number of SASTM-based tools (e.g., macros for the analyses of AE data or laboratory data; Report Appendix Generator system (RAGe) for compilation/formatting of the CTR appendices).

PK parameters will be calculated using Phoenix WinNonlinTM software (version Phoenix 6.3, [REDACTED]).

4. CHANGES IN THE PLANNED ANALYSIS OF THE STUDY

In addition to the CTP-described analysis summary statistics as well as profile plots will be provided for the primary and secondary endpoint.

All other analyses described in this TSAP are in accordance with the statistical methods described in the revised CTP.

5. ENDPOINTS

5.1 PRIMARY ENDPOINTS

The primary endpoint of BI 409306, BI 425809, lamotrigine and placebo is as named in Section 2.1.2 and defined in Section 5.4.1.1 of the CTP:

- *PAL Total Errors Adjusted (PALTEA28) on ketamine*

5.2 SECONDARY ENDPOINT

5.2.1 Key secondary endpoints

Not applicable.

5.2.2 Secondary endpoint

The secondary endpoints of BI 409306, BI 425809, lamotrigine and placebo are as named in Section 2.1.3 and defined in Sections 5.4.1.2 and 5.4.1.3 of the CTP:

- *SWM Between Errors (SWMBE468) on ketamine*
- *RVP A' Prime (RVPA) on ketamine*

[figure not shown]
5.3.1 Safety parameters

[figure not shown]
Safety and tolerability of BI 409306, BI 425809, lamotrigine, placebo and ketamine will be assessed based on further safety parameters named in Section 2.2.2.3 and defined in Section 5.2 of the CTP:

[figure not shown]
- *Adverse events (including clinically relevant findings from the physical examination incl. targeted examination, visual acuity test, vital signs; as well as clinically relevant abnormal results in C-SSRS and safety tests (DSST, MOAA/S, CADSS and SFST))*
- *Safety laboratory tests (only abnormal findings will be reported as AEs)¹*
- *12-lead ECG and continuous ECG monitoring (only abnormal findings will be reported as AEs)*
- *Vital signs (BP, PR, SaO₂)²*
- *Suicidality assessment (C-SSRS)*

¹ According to the CTP Section 5.2.3 safety laboratory test results will only be kept in the source data but not collected in the CRF. Clinically relevant abnormal findings will be reported as AEs.

² According to the CTP Section 5.2.2 SaO₂ will only be kept in the source data but not collected in the CRF. Clinically relevant abnormal findings will be reported as AEs.

6. GENERAL ANALYSIS DEFINITIONS

6.1 TREATMENTS

For basic study information on treatments to be administered, assignment of treatment groups, and selection of doses, cf. Section 4 of the CTP.

Each subject is planned to be treated in three subsequent treatment periods with one single dose at Day 1 in each treatment period:

- Test treatment 1 (T1):
300 mg of Lamotrigine as tablet
- Test treatment 2 (T2):
[REDACTED] of BI 409306 as film-coated tablet
- Test treatment 3 (T3):
[REDACTED] of BI 425809 as film-coated tablet
- Reference treatment (R):
Placebo as film-coated tablet

Each subject is planned to be randomly allocated to one of 18 3-period sequences including placebo in one of the periods and 2 out of 3 active treatments in the remaining periods:

T1–T2–R, T1–R–T2, T1–T3–R, T1–R–T3, T2–T1–R, T2–R–T1, T2–T3–R, T2–R–T3, T3–R–T1, T3–T1–R, T3–T2–R, T3–R–T2, R–T1–T2, R–T2–T1, R–T1–T3, R–T3–T1, R–T2–T3, R–T3–T2.

Each treatment period is separated by a washout period of at least 11 days.

[REDACTED] : *The Residual Effect Period (REP)* [REDACTED]
[REDACTED], for lamotrigine 10 days, and for ketamine 24 hours. This is the period
after the last dose with measurable drug levels and/or pharmacodynamic effects is still likely
to be present.

For statistical analyses of AEs and vital signs, the following separate analysis phases will be defined for each subject:

Table 6.1: 1 Analysis phases for statistical analysis of AEs and actual treatment for analysis of vital signs

Study analysis phase	Label of analysing treatment	Label of actual treatment	Start	End
Screening	Screening	Screening	Date of informed consent	Start date/time of screening ketamine infusion
		Screening+Ketamine	Start date/time of screening ketamine infusion	End date/time of screening ketamine infusion + 24 h
		Screening	End date/time of screening ketamine infusion + 24 h	Start date/time of first administration of study treatment (Planned time: 00:00h) in the respective treatment period
On treatment ^{1, 2, 3}	Placebo, [REDACTED] BI 409306, BI 425809 or 300mg Lamotrigine, respectively	Placebo, [REDACTED] BI 409306, BI 425809 or 300mg Lamotrigine, respectively	Start date/time of administration of the first study treatment (Planned time: 00:00h) in the respective treatment period	Start date/time of on-treatment ketamine infusion or 12:00 a.m. on day after subject's trial completion date, whatever comes first
	Placebo+Ketamine, [REDACTED] BI 409306+Ketamine, [REDACTED] BI 425809+Ketamine or 300mg Lamotrigine+Ketamine, respectively	Start date/time of on-treatment ketamine infusion	End date/time of on-treatment ketamine infusion + 24 h or 12:00 a.m. on day after subject's trial completion date, whatever comes first	
	Placebo, [REDACTED] BI 409306, BI 425809 or 300mg Lamotrigine, respectively	End date/time of on-treatment ketamine infusion + 24 h	Start date/time of administration of the second study treatment (Planned time: 03:00h) in the respective treatment period + 11 days * 24 h/day (for BI 409306, BI 425809, lamotrigine and placebo) or Date/time of administration of study drug in the next treatment period or 12:00 a.m. on day after subject's trial completion date, whatever comes first	
Follow-up	F/U Placebo, F/U [REDACTED] BI 409306, F/U [REDACTED] BI 425809 or F/U 300mg Lamotrigine, respectively	F/U Placebo, F/U [REDACTED] BI 409306, F/U [REDACTED] BI 425809 or F/U 300mg Lamotrigine, respectively	Start date/time of administration of the second study treatment (Planned time: 03:00h) in the respective treatment period + 11 days * 24 h/day (for BI 409306, BI 425809, lamotrigine and placebo)	Date/time of administration of the respective treatment in the next treatment period, if applicable, or 12:00 a.m. on day after subject's trial completion date, whatever comes first.

¹ See [Section 6.7](#) for definition of baseline, which will be used in the statistical analyses of vital signs.

² A REP of 11 days will be used for all study treatments (BI 409306, BI 425809, lamotrigine and placebo) to avoid any bias which might occur due to different observation times. This may lead to an overestimation of AEs in the treatment periods in which subjects received a study treatment with considerably lower REP.

³ The on-treatment phase extends from Day 1 00:00h (planned time) to Day 11 03:00h (planned time) to include AEs which occur after the start of the first study drug (or corresponding placebo) administration (which is not necessarily the analysing treatment of the respective treatment period) as well as AEs which occur within the REP of the second study drug (or corresponding placebo).

Analysis phases for statistical analysis of AEs are defined for each subject as described in [Table 6.1: 1](#).

AE summary tables will present results for the on-treatment phase only. All AEs will be listed.

In AE tables in CTR Section 15.3 (but not in displays for ClinicalTrials.gov) the following total will be provided in addition:

- **"Total on-trt"**, defined as the total over all on-treatment phases

Listings of AEs presented in Section 15.4 will display results for the screening, on-treatment and follow-up phases (labelled with the name of the study treatment (short label)).

AE tables and listings will be displayed by analysing treatment. Beyond that, listings will include an additional column for the actual treatment (defined in Table 6.1: 1).

Vital signs, ECG, CANTAB, [REDACTED] will be analysed based on the respective treatment (Placebo, BI 409306, BI 425809 or Lamotrigine) with clear differentiation between baseline (cf. [Section 6.7](#)) and post-baseline measurements. Measurements will be considered on-treatment, if they were taken within the on-treatment phases as defined in Table 6.1: 1. ECG measurements are considered to be on-treatment if they were measured between the first administration of the respective treatment and the corresponding residual effect period after the last administration of the respective treatment.

Vital signs listings will include an additional column for the actual treatment (defined in Table 6.1: 1).

More details on the technical implementation of these analyses are provided in the ADS Plan of this TSAP.

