7.2.5 Safety analyses

Adverse events will be coded using the Medical Dictionary for Drug Regulatory Activities (MedDRA). Standard BI summary tables and listings will be produced. All adverse events with an onset between start of treatment and end of the REP, a period of 11 days after the last dose of randomised trial medication, will be assigned to the on-treatment period for evaluation.

The safety analysis will be done by 'treatment at onset'.

All treated patients will be included in the safety analysis. In general, safety analyses will be descriptive in nature and will be based on BI standards. No hypothesis testing is planned.

Statistical analysis and reporting of adverse events will concentrate on treatment-emergent adverse events, i.e. all adverse events occurring between start of treatment and end of the REP. Adverse events that start before first drug intake and deteriorate under treatment will also be considered as 'treatment-emergent'.

Frequency, severity, and causal relationship of adverse events will be tabulated by system organ class and preferred term after coding according to the current version of the Medical Dictionary for Drug Regulatory Activities (MedDRA) at database lock.

Vital signs, physical examinations, or other safety-relevant data observed at screening, baseline, during the course of the trial and at the end-of-trial evaluation will be assessed with regard to possible changes compared to findings before start of treatment.

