6.3 SUBJECT SETS ANALYSED

Subject sets will be used as defined in Section 7.2.1 of the CTP:

- **Treated set (TS):**
The treated set includes all subjects who were randomized and treated with at least one dose of study drug or ketamine. The treated set will be used for safety analyses.
- **Pharmacodynamic set (PDS):**
PD analyses will be based on the PDS which is defined as all randomised patients who performed the post ketamine tests in at least one period.

The following additional subject sets will be used:

- **Screened set (SCS):**
This set includes all subjects who signed the informed consent form.

[figure not shown]

Table 6.3: 1 Subject sets analysed

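### SAP Table 6.1: 1 has no workable end rule for the on-treatment AE phase when study drug is given without ketamine, and it conflicts with its own footnotes

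*SAP*

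**What the plan says.** SAP 6.1 assigns AEs to phases through Table 6.1: 1 and shows only the on-treatment phase in the AE summary tables. The table builds that phase from three rows, called here pre-ketamine, ketamine and post-ketamine.

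- **Pre-ketamine row.** It starts at the first study drug (planned time 0:00) and ends at "Start date/time of on-treatment ketamine infusion or 12:00 a.m. on day after subject's trial completion date, whatever comes first".
- **Post-ketamine row.** It starts at "End date/time of on-treatment ketamine infusion + 24 h". It ends at the earliest of three times: "Start date/time of administration of the second study treatment (Planned time: 03:00h) in the respective treatment period + 11 days * 24 h/day"; "Date/time of administration of study drug in the next treatment period"; or the trial-completion limit.
- **Follow-up row.** It starts at the second study treatment + 11 days, whether or not ketamine was given.

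Other text limits the phase as a whole. Footnote 2 says "A REP of 11 days will be used for all study treatments (BI 409306, BI 425809, lamotrigine and placebo) to avoid any bias" from unequal observation times. Footnote 3 runs the on-treatment phase from Day 1 00:00h to Day 11 03:00h, planned time. SAP 7.8.1 repeats the 11-day residual effect period (REP) for all treatments. Protocol 7.2.5 takes the on-treatment period to the "end of the REP, a period of 11 days after the last dose of randomised trial medication". A man belongs to the Treated Set once "treated with at least one dose of study drug or ketamine" (SAP 6.3).

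**The concern.** In a planned session ketamine starts 5 h after the first dose, so the trial-completion alternative in the pre-ketamine row can only take effect when ketamine is not given. In that case the post-ketamine row never opens, and the 11-day and next-period limits it carries never apply. From the second dose + 11 days, the same AE fits both the on-treatment and the follow-up phase.

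A second gap concerns a man who takes the 0:00 dose but not the 3:00 dose. He is in the Treated Set, yet the table's 11-day limit and its follow-up start both hang on a second study treatment that he never took.

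At stake is which AEs enter the summary tables, and under which treatment. The same phases also decide which vital signs count as on-treatment (SAP 6.1) and which medications are concomitant to a period (SAP 7.2).

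**Working it through.** **Inputs.** Hours run from planned time 0:00 on Day 1, which is 08:00 by the clock (protocol Flow Chart D). The first dose is at 0 h, the second at 3 h and ketamine at 5 h. The REP is 11 days (Table 6.1: 1, footnote 2). Washout is at least 11 days between drug administrations (protocol synopsis). The end-of-trial examination is on Day 12 to 19 (Flow Chart A). The trial completion date is taken as the date of that examination.

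**Step 1: the plan's own end point.**
- Table: 3 + 11 x 24 = 267 h, which is Day 12 03:00.
- Footnote 3: Day 11 03:00 = 10 x 24 + 3 = 243 h.
- Difference: 267 - 243 = 24 h. The two would agree only if the dosing day were Day 0, but footnote 3 and the protocol call it Day 1.

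**Step 2: drug given, no ketamine, man stops.** The row ends at the midnight after the examination day, which is 16 h after 08:00 on that day.
- Examination on Day 12: 11 x 24 + 16 = 280 h; 280 - 267 = 13 h past the REP.
- Examination on Day 19: 18 x 24 + 16 = 448 h; 448 - 267 = 181 h = 7 d 13 h past the REP.
- Examination at discontinuation, as protocol 3.3.4 asks where possible: the row can close before 267 h, with no overrun.

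**Step 3: drug given, no ketamine, man continues.** The end cell does not tie the infusion to the respective treatment period, so there are two readings.
- *The next period's infusion closes the row.* At minimum washout: 11 x 24 + 5 = 269 h, which is 2 h past the REP and 5 h into the next period. At an assumed 14-day washout: 14 x 24 + 5 = 341 h, which is 74 h past the REP.
- *Only that period's infusion counts.* The row runs to trial completion. With minimum washouts, Period 3 starts 22 days after Period 1 and 11 days after Period 2, and the examination falls 11 to 18 days after the Period 3 dose. From Period 1 the window is 22 + 11 = 33 to 22 + 18 = 40 days. From Period 2 it is 11 + 11 = 22 to 11 + 18 = 29 days. Counted to the closing midnight, the overrun past the REP is 22 d 13 h to 29 d 13 h from Period 1, and 11 d 13 h to 18 d 13 h from Period 2.

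**Step 4: second dose not taken.** The table's anchor does not exist. The last-dose rule of protocol 7.2.5 still works: 0 + 264 h = Day 12 00:00.

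**Step 5: weight of one man.** One man newly counted for an AE term moves an active-treatment rate by 1/24 = 4.2 percentage points and the placebo rate by 1/36 = 2.8. The documents do not say how many sessions would be affected. If 0 to 5% of the 36 x 3 = 108 sessions is assumed, that is 0 to 5 sessions.

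**The case against.** The strongest reply is that the SAP already bounds the phase. Footnotes 1 to 3 hang on the on-treatment label, so they can be read as governing all three rows, and footnote 3 carries no ketamine condition. Follow-up starts on the same clock with or without ketamine. AE tables go by analysing treatment; actual treatment is only an extra listing column, so the rows may be meant merely to split one phase. The trial-completion limit recurs in every on-treatment and follow-up row and fits a man who drops out before ketamine. Safety analysis is descriptive, all AEs are listed, and implementation details sit in an ADS Plan that was not supplied.

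Most of this stands, and it rules out a stronger reading. A reader might infer that the SAP settles on a window running weeks past the REP, so that later ketamine reactions are counted under an earlier drug. The documents do not support that. It needs the second reading in Step 3, precedence of one table cell over the 11-day rules and over analysis by treatment at onset (protocol 7.2.5), and a man who takes drug, gets no ketamine and continues. The documents do not describe that path, and several reasons for withholding ketamine could also meet the discontinuation criteria in protocol 3.3.4.1.

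The reply does not remove the conflict. The SAP points to the table for each subject's phases and gives no rule for when table and footnotes disagree. Footnote 3 cannot settle it, because its own end differs from the table's by 24 h. Protocol 7.2.5 supplies an anchor when the 3:00 dose is missed, but the table does not use it.

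**Conclusion.** The point holds as an internal conflict and an unhandled case. For a session with study drug and no ketamine, Table 6.1: 1 as written lacks the 11-day limit, overlaps follow-up and disagrees with footnotes 2 and 3, SAP 7.8.1 and protocol 7.2.5. When the second dose is not taken, the table gives neither an 11-day limit nor a follow-up start. Footnote 3 needs correcting in any case.

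Severity is minor. The overrun depends on the reading: none, or 13 h to 7 d 13 h, for a man who stops; 2 h at minimum washout, or up to trial completion, for a man who continues. These figures assume minimum washouts (except the 14-day example) and trial completion on the day of the examination. Planned sessions and the primary endpoint are unaffected. The share of affected sessions is an assumption that includes zero, and the ADS Plan may already handle the case.

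**What to change.** In Table 6.1: 1, define the end of the on-treatment phase once for all three rows, as the earliest of:

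- the last study-drug or matching-placebo dose actually taken in that period + 11 x 24 h;
- the first dose of the next period;
- the existing trial-completion limit.

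Start follow-up at that same time. Let ketamine start and stop times only split the phase into actual-treatment labels, and tie the infusion to the respective period. Bring footnote 3 into line with the table. A session without ketamine would then close no later than Day 12 03:00, or at Day 12 00:00 if the next dose comes at the minimum washout.

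The cost is a few table cells, one footnote and the matching derivation in the ADS Plan. Every limit is already in the documents, and no new data are needed.
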